1.5. Benefit-risk Assessment

Subjects in the current study will not receive any health benefit (beyond that of an assessment of their medical status) from participating in the study.

The risks of participation are primarily those associated with adverse reactions to the study treatments, although there may also be some discomfort from collection of blood samples and other study procedures. More information about the known and expected benefits, risks, and reasonably anticipated AEs associated with LOXO-292 may be found in the current IB.¹

The dose of ranitidine administered in this study is not anticipated to induce any significant potential risk or benefit to subjects participating in this study, as the multiple doses are administered according to the dosing recommendations found in the full prescribing information for ranitidine.⁵

The dose of omeprazole administered in this study is not anticipated to induce any significant potential risk or benefit to subjects participating in this study, as the multiple doses are administered according to the dosing recommendations found in the full prescribing information for omeprazole.⁶

The safety monitoring practices employed by this protocol (ie, 12-lead electrocardiogram [ECG], vital signs, clinical laboratory tests, AE questioning, and physical examinations [PEs]) are adequate to protect the subjects' safety.

2. OBJECTIVES AND ENDPOINTS

2.1. Objectives

The objectives of this study are:

Primary:

- To assess the effect of multiple doses of an H2 antagonist (ranitidine) administered with a single dose of LOXO-292 on the PK of LOXO-292 under fasted conditions in healthy adult subjects.
- To assess the effect of multiple doses of a PPI (omeprazole) administered with a single dose of LOXO-292 on the PK of LOXO-292 given with a low-fat meal in healthy adult subjects.

Secondary:

- To determine the safety and tolerability of a single dose of LOXO-292 under fasted conditions alone, in combination with an H2 antagonist (ranitidine) under fasted conditions, and in combination with a PPI (omeprazole) given with a low-fat meal in healthy adult subjects.

2.2. Endpoints

The following PK parameters will be calculated whenever possible, based on the plasma concentrations of LOXO-292 (as appropriate): area under the concentration-time curve from Hour 0 to the last measurable concentration (AUC_{0-t}), area under the concentration time curve extrapolated to infinity ($AUC_{0-\infty}$), extrapolation for area under the concentration time curve ($\%AUC_{\text{extrap}}$), maximum plasma concentration (C_{max}), t_{max} , elimination rate constant (λ_Z), apparent systemic clearance (CL/F), and apparent terminal elimination half-life ($t_{\frac{1}{2}}$).

Safety and tolerability will be assessed by monitoring AEs, performing PEs and clinical laboratory tests, measuring vital signs, and recording ECGs.

3. INVESTIGATIONAL PLAN

3.1. Overall Study Design and Plan

This is an open label, 3-period, fixed sequence study.

In Period 1, a single oral dose of LOXO-292 will be administered under fasted conditions. On Day 1 of Period 1, a single oral dose of 160 mg of LOXO-292 will be administered following a fast of 10 hours prior to and 4 hours after the LOXO-292 dose. Blood samples for LOXO-292 PK analysis will be taken for 168 hours after the LOXO-292 dose on Day 1.

In Period 2, multiple oral doses of ranitidine will be administered twice daily from Day 8 until Day 18 inclusively (for a total of 11 consecutive days) and administered with a single oral dose of LOXO-292 on Day 12 under fasted conditions. On Day 12, a single oral dose of 160 mg of LOXO-292 will be administered following a fast of 10 hours prior to and 4 hours after the LOXO-292 dose. On Day 12, ranitidine will be administered 2 hours (\pm 10 minutes) after the LOXO-292 dose. On Days 8-11 and 13-18, the morning dose of ranitidine will be administered (with breakfast) approximately 2 hours (\pm 1 hour) after the planned or actual time of the Day 12 LOXO-292 dose and the evening dose of ranitidine will be administered (with a light meal/snack) approximately 10 hours (\pm 1 hour) prior to the planned or actual time of the Day 12 LOXO-292 dose. Blood samples for LOXO-292 PK analysis will be taken for 168 hours after the LOXO-292 dose on Day 12.

In Period 3, multiple oral doses of omeprazole will be administered once daily from Day 19 until Day 29 inclusively (for a total of 11 consecutive days) and administered with a single oral dose of LOXO-292 on Day 23 with a low-fat meal. On Day 23, omeprazole and a single oral dose of 160 mg of LOXO-292 will be coadministered within 30 minutes of the start of a low-fat meal, which will be entirely consumed within 30 minutes. On Days 19 - 22 and 24 - 29, omeprazole will be administered following a fast of 2 hours prior to and 1 hour after the omeprazole dose (Note: omeprazole will be administered at approximately the actual time of the Day 12 LOXO-292 dosing). Blood samples for LOXO-292 PK analysis will be taken for 168 hours after the LOXO-292 dose on Day 23.

There will be a washout period of 7 days between the LOXO-292 dose in Period 1 and the first dose of ranitidine in Period 2 and a washout period of 7 days between the LOXO-292 dose in Period 2 and the first dose of omeprazole in Period 3.

To assess their eligibility to enter the study, potential subjects will be screened within 28 days (Days -29 to -2) and be admitted to the Clinical Research Unit (CRU) on Day -1 (Check-in). Replacement subjects may be enrolled only if deemed necessary by the Sponsor.

Subjects will be confined at the CRU from the time of Check-in (Day -1) until End of Treatment (EOT) on Day 30 upon completion of all PK and safety assessments or Early Termination (ET) if the subject discontinues. A follow-up phone call will occur for all subjects who received at least 1 dose of study drug (including subjects who are terminated early) 7 days (\pm 2 days) after EOT or ET.

The start of the study is defined as the date the first subject who is enrolled in the study signs an Informed Consent Form (ICF). Note that enrolled subjects are defined as those subjects who are assigned a dose of study drug; this definition excludes screen failure subjects.

In this study, PEs, 12-lead ECGs, vital signs, How Do You Feel? (HDYF?) inquiries, clinical chemistry panel, coagulation parameters, complete blood count (CBC), and urinalysis (UA; [Appendix 2](#)) and recording of concomitant medications will be performed at specified times during the study (for specific timepoints and details on each study variable, refer to [Appendix 4](#)). AEs and SAEs will be collected beginning at informed consent. AEs will be reported throughout the study (ie, from signing of the ICF until End of Study [EOS], or until ET if the subject discontinues from the study and does not complete a follow-up phone call), either as subject medical history (if the event is reported as beginning prior to signing of the ICF or if the event occurs prior to study drug administration on Day 1 and is assessed as not related to study procedures by the Investigator [or designee]) or as AEs (if the event occurs after signing of the ICF but prior to study drug administration on Day 1 and is assessed as related to study procedures by the Investigator [or designee], or if the event occurs after study drug administration on Day 1 through EOT or ET regardless of relationship to study drug). From EOT or ET through EOS, only AEs assessed as related to study drug by the Investigator (or designee) are to be reported. All SAEs that develop from the time of ICF signing until EOS (or ET, if the subject discontinues from the study and does not complete a follow-up phone call) are to be reported.

Blood samples for LOXO-292 PK analysis will be obtained in each period through 168 hours following LOXO-292 administration. A study flow chart is presented in [Appendix 4](#). Study completion is defined as the time of the last subject's follow-up phone call.

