1.4. Study Rationale

LOXO-292 has pH-dependent solubility and its PK can be affected by agents that modify gastric pH such as proton pump inhibitors (eg, omeprazole). Under fasted conditions, following a single dose of 160 mg LOXO-292 administered to 20 omeprazole-treated healthy volunteers, the area under the concentration-time curve (AUC) and C_{max} of LOXO-292 were approximately 69% to 88% lower than following administration of LOXO-292 under fasted conditions without omeprazole. The effect of an H2 antagonist on the PK of LOXO-292 has not been tested.

In contrast to omeprazole, which is an irreversible inhibitor of gastric acid secretion, ranitidine has a shorter duration of action. This study will test the effect of ranitidine when given 10 hours before and 2 hours after the dose of LOXO-292.

The effect of omeprazole on the PK of LOXO-292 is reduced or eliminated when LOXO-292 is given with a high-calorie, high-fat meal. The AUC of LOXO-292 following administration of a single dose of 160 mg with a high-calorie, high-fat meal to 20 omeprazole-treated healthy volunteers was approximately 2% higher than following 160 mg LOXO-292 given under fasted conditions without omeprazole, although C_{max} was approximately 49% lower. Therefore, during Period 3, LOXO-292 will be administered with a low-fat meal.

To determine if the effect of agents that modify gastric pH on the PK of LOXO-292 can be reduced by various antacid dosing regimens, this study will evaluate the effect of multiple doses of an H2 antagonist (ranitidine) administered with a single dose of LOXO-292 administered under fasted conditions and the effect of multiple-doses of a proton pump inhibitor (PPI) (omeprazole) administered with a single dose of LOXO-292 given with a low-fat meal on the PK of LOXO-292 in healthy adult subjects.

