10.3.3 Pharmacokinetic Statistical Methodology

A statistical analysis will be conducted to investigate the drug-drug interaction on the PK of LOXO-292 for AUC_{0-t} , $AUC_{0-\infty}$ and C_{max} . The comparisons of interest are:

- LOXO-292 (fasted) co-administered with ranitidine vs LOXO-292 (fasted)
- LOXO-292 (fed) co-administered with omeprazole vs LOXO-292 (fasted)

The primary analysis planned for this study is an Analysis of Variance (ANOVA) model that includes treatment as a fixed-effect and subject as a random-effect. CCI

[REDACTED]

[REDACTED]

CCI

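### Does the snack taken with the Day 11 evening ranitidine dose undermine the fasted ranitidine comparison?

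*Protocol*

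**What the plan says.** Protocol 3.1 sets two rules for the night before the only LOXO-292 dose of Period 2.

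- **Ranitidine:** on Days 8-11 and 13-18, "the evening dose of ranitidine will be administered (with a light meal/snack) approximately 10 hours" before the planned or actual Day 12 LOXO-292 time, with a tolerance of 1 hour either way.
- **Fast:** "On Day 12, a single oral dose of 160 mg of LOXO-292 will be administered following a fast of 10 hours prior to" dosing, continued for 4 hours afterwards. No tolerance is given.

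The same pair of rules appears in the protocol synopsis, Protocol 5.2 and 6.2, Appendix 4 (footnotes i and j) and SAP 6. Protocol 1.4 gives the purpose: "This study will test the effect of ranitidine when given 10 hours before and 2 hours after the dose of LOXO-292". The first comparison of interest in SAP 10.3.3 is "LOXO-292 (fasted) co-administered with ranitidine vs LOXO-292 (fasted", so both periods in that contrast carry the fasted label. Period 1 has the same 10-hour fast.

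For Day 12 itself, the text places one ranitidine dose 2 hours (within 10 minutes) after LOXO-292. It gives no clock time for an evening dose that day, although the regimen is twice daily through Day 18.

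**The concern.** The snack window is centred on the moment the fast has to begin. Half of it, or more once eating time is counted, lies inside the fasting period, and even a snack started at the nominal 10 hours leaves slightly less than a 10-hour fast. No section gives the fast a tolerance, exempts the Day 11 snack or says which rule prevails.

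If subjects were dosed late in the window, Period 2 would carry a slightly shorter fast than its label says, in a contrast whose objective specifies fasted conditions. SAP 9 says that deviations are weighed when populations are assigned but has no rule for a short fast, so a unit following the ranitidine window to the letter might generate deviations needing case-by-case decisions in a study of 20 subjects.

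Two lesser points add to the impression of loose drafting. The dose 10 hours before LOXO-292 has a tolerance of 60 minutes, against 10 minutes for the dose 2 hours after it. The Day 12 text names one ranitidine dose in a twice-daily regimen.

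**Working it through.** The documents give no figure to reproduce here. The sample-size sections are redacted, and the point does not depend on them.

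**Inputs**

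- Permitted ranitidine and snack start, T: 9 to 11 hours before LOXO-292, a window of 120 minutes (Protocol 3.1).
- Required fast: 10 hours (Protocol 3.1; Appendix 4 footnote i).
- Snack duration, s hours: not stated. I assume 0, 10, 15 or 30 minutes.

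**Formulae**

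The fast is met if T - s >= 10.

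Share of the window leaving a short fast = (10 + s - 9) / (11 - 9).

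Shortest permitted fast = 9 - s.

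Time in the window meeting both rules = 120 minutes x (1 - share).

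| Assumed snack duration | Share with short fast | Shortest fast | Window meeting both rules |
|---|---|---|---|
| 0 min | 1.000/2 = 50% | 9.0 h | 60 min |
| 10 min | 1.167/2 = 58% | 8.83 h | 50 min |
| 15 min | 1.250/2 = 62.5% | 8.75 h | 45 min |
| 30 min | 1.500/2 = 75% | 8.5 h | 30 min |

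The overlap is therefore real, and 50% is its minimum. The last column matters as much: even with a 30-minute snack, a half-hour slot satisfies both rules. The texts permit a short fast but do not force one. The percentages are shares of a clock window and do not predict how many subjects would be affected.

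**Can the unit use that slot?** Subjects are confined from Day -1 to Day 30 (Protocol 3.1). Site staff supervise every dose (Protocol 5.5). The diet is standardized and timed so as not to clash with other study activities (Protocol 6.2). Actual dose times are recorded (Protocol 5.2). Snack timing is thus in the unit's hands, and a late Day 11 dose would be visible in the data.

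**Could a short fast move the ratio?** The only food data in the protocol (1.4) concern a high-calorie, high-fat meal given with LOXO-292 in omeprazole-treated volunteers. They say nothing about a light snack about 9 hours earlier followed by the full 4-hour post-dose fast. No size of bias can be derived from the documents.

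**Do the two periods differ?** Protocol 3.1 ties no drug-linked snack to the evening of Day -1, but subjects are already in the unit on its diet and that evening's menu is not given. A snack before Period 1 is neither prescribed nor excluded, so a prandial difference cannot be inferred.

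**Day 12 evening dose.** Protocol 3.1 and the synopsis state twice-daily ranitidine through Day 18, and SAP 7 labels the treatment as twice daily, so the dose is implied. At the usual evening clock time it would fall 24 - 10 = 14 hours after LOXO-292 (13 to 15 with the tolerance). The median time to peak is about 2 hours (Protocol 1.3, patient data).

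**The case for a change.** The strongest case for acting is that the contradiction is visible on the page, is repeated in six places and would cost only a text clarification. Fasted conditions are part of the first primary objective, and the interval of 10 hours before LOXO-292 is part of the regimen being tested. The Day 11 dose can be timed only to the planned LOXO-292 time. Dose times may be staggered between subjects (Protocol 5.2), so a LOXO-292 dose given earlier than planned would shorten the fast further. Settling the wording before dosing is better than judging deviations afterwards.

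The overlap stands as a drafting fault, as does the missing clock time for the Day 12 evening dose. The step from there to a weakened comparison does not hold. The fast is a separate, explicit requirement, and the ranitidine window does not authorise breaking it. A unit bound by both would time the snack in the part of the window where they agree, still within the tolerance the protocol accepts for the 10-hour interval. If a breach occurred, SAP 9 provides for it to be considered before database lock; a specific rule for a fast less than an hour or so short would add little without evidence that it matters. The unequal tolerances are a matter of preference: no section shows that an hour either way at a nominal 10 hours changes the result, and a tighter limit close to the absorption peak is understandable.

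**Conclusion.** No change to the plan follows. The Day 11 snack window and the Day 12 fast overlap for at least 60 of 120 minutes, and the largest permitted shortfall is 1 hour plus eating time (1.5 hours if a 30-minute snack is assumed). Both rules can still be met together, with 30 to 60 minutes of the window left over the assumed snack durations of 0 to 30 minutes. A site following both as written would obtain a sound ranitidine-to-alone ratio from the planned model.

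This rests on two assumptions: that the unit uses the control over meals and dosing that the protocol gives it, and that a fast of about 8.5 to 9 hours after a light snack behaves much like a 10-hour one. The documents do not test the second, but nothing in them points the other way. The Day 12 evening dose is a missing detail that the stated twice-daily regimen fills.

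Reconciling the passages is an editorial matter for the sponsor and investigator, and which text gives way is theirs to decide. It would not alter the estimand, model, populations or any planned result.

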3.2. Discussion of Study Design

This study will evaluate the effect of multiple doses of an H2 antagonist (ranitidine) administered under fasted conditions and the effect of effect of multiple-doses of a PPI (omeprazole) given with a low-fat meal on the PK of LOXO-292 in healthy adult subjects.

Gastric pH can alter the absorption of acidic and basic drugs and nonclinical study results indicate that LOXO-292 may be sensitive to gastric pH. The Food and Drug Administration (FDA) has recently published a review on the topic and has encouraged studies to address the effects of coadministration of gastric pH modifiers on oral exposure.⁷ Thus, a PPI and an H2 antagonist were chosen to be studied.

Subjects will participate in 3 periods in a fixed sequence. The washout period of 7 days between LOXO-292 doses is considered sufficient to prevent carryover effects of the treatments. However, as omeprazole may have a prolong effect on acid secretion due to the irreversible nature of omeprazole binding to H⁺/K⁺ ATPase pump, the omeprazole treatment portion will be conducted only in Period 3 to ensure the effect of a PPI with a low-fat meal can be assessed without confounding factors.

3.3. Selection of Doses in the Study

LOXO-292

An oral dose has been selected for this study because this is the intended clinical route of administration. The dose of 160 mg of LOXO-292 was selected based on clinical study results and its observed PK profile. The 160 mg dose is expected to ensure sufficient quantifiable plasma concentrations of LOXO-292 for determination of systemic PK exposure. In a Phase 1/2 clinical study in cancer patients (LOXO-RET-17001), 160 mg of LOXO-292 dosed twice daily has been evaluated and has been selected for further testing in a larger number of cancer patients to evaluate its safety and efficacy.

Omeprazole:

A dose of 40 mg omeprazole daily is within the recommended dose as prescribed in the labeling. In addition, multiple doses for 4 consecutive days prior to LOXO-292 administration will ensure maximum inhibition of acid secretion by omeprazole, because the inhibitory effect of omeprazole on acid secretion increases with repeated once-daily dosing, reaching a plateau after 4 days.

Ranitidine:

A dose of 150 mg ranitidine twice daily is within the recommended dose as prescribed in the labeling. In addition, multiple doses for 4 consecutive days prior to LOXO-292 administration will mimic real-life scenarios of patients taking H2 antagonists in the intended patient population.

4. SELECTION OF STUDY POPULATION

The study will be conducted in healthy subjects. As per the recommendations of the FDA in the draft guidance on clinical drug interaction studies,⁸ drug interaction studies can be carried out in healthy volunteers assuming that findings in healthy subjects can be used to predict findings in the intended patient population.

4.1. Screening Procedures

The following screening procedures will be performed for all potential subjects at a visit conducted within 28 days of study entry (ie, prior to Check-in [Day -1]):

1. Informed consent
2. Demographic data
3. Medical history
4. Inclusion/exclusion criteria
5. Height, weight, and body mass index (BMI)
6. Complete PE ([Section 7.2.5](#))

7. Screens for hepatitis C virus (HCV) antibody, hepatitis B surface antigen (HBsAg), and human immunodeficiency virus (HIV) antibody ([Appendix 2](#))
8. Screen for selected drugs of abuse (including cotinine) and an alcohol breath test ([Appendix 2](#))
9. Twelve-lead ECG measured after the subject has been resting in the supine position for at least 10 minutes ([Section 7.2.4](#))
10. Vital signs (including oral temperature, respiratory rate, and supine blood pressure [BP] and heart rate [HR; measured after the subject has been supine for at least 5 minutes]) ([Section 7.2.3](#))
11. Clinical laboratory evaluations ([Section 7.2.2](#); clinical chemistry panel [fasted at least 8 hours], coagulation parameters, creatine kinase (CK), CBC, and UA; [Appendix 2](#))
12. Hemoglobin A1c test ([Appendix 2](#))
13. Thyroid stimulating hormone (TSH) test ([Appendix 2](#))
14. How Do You Feel? inquiry and AE and concomitant medication evaluations ([Section 7.2.1](#))
15. Serum pregnancy test (for females only; [Appendix 2](#))
16. Follicle-stimulating hormone (FSH) test (for postmenopausal females only; [Appendix 2](#))

4.2. Check-in Procedures (Day -1)

At Check-in (Day -1), subjects will report to the CRU and the following procedures will be performed:

1. AEs
2. Interim medical history
3. Weight and BMI
4. Abbreviated PE ([Section 7.2.5](#))
5. Review of inclusion/exclusion criteria
6. Screen for selected drugs of abuse (including cotinine) and an alcohol breath test ([Appendix 2](#))
7. Twelve-lead ECG measured after the subject has been resting in the supine position for at least 10 minutes ([Section 7.2.4](#))
8. Vital signs (including oral temperature, respiratory rate, and supine BP and HR [measured after the subject has been supine for at least 5 minutes]) ([Section 7.2.3](#))

9. Clinical laboratory evaluations ([Section 7.2.2](#); clinical chemistry panel [fasted at least 8 hours], including CK, coagulation parameters, CBC, and UA; [Appendix 2](#))
10. TSH test ([Appendix 2](#))
11. How Do You Feel? inquiry and concomitant medication evaluations ([Section 7.2.1](#))
12. Serum pregnancy test (for females only; [Appendix 2](#))
13. Follicle-stimulating hormone (FSH) test (for postmenopausal females only; [Appendix 2](#))
14. Compliance with concomitant medications and exclusionary restrictions ([Section 6](#))

For subjects to continue their participation in the study, the inclusion/exclusion criteria must continue to be met at Day -1 (as appropriate; [Section 4](#)). In addition, continued compliance with concomitant medication and other restrictions will be verified.

The Sponsor will review medical history and all screening evaluations for potential subjects prior to enrollment. Prior to dosing, the Sponsor will provide approval of subjects selected for enrollment by the Investigator (or designee).

Subjects who meet all the inclusion criteria and for whom none of the exclusion criteria apply will be eligible to be enrolled into the study. Safety evaluations may be repeated at the discretion of the Investigator (or designee) or Sponsor.

